5.8 Other Analyses

- To explore the relationship between LAA closure rate and other endpoints, effective LAA closure rate at 45 days and 6 months will be used to classified other endpoints.
- Descriptive analysis will be used for other analysis.
- To explore the relationship between all bleedings, the descriptive of TTR (Time in Therapeutic Range), and an appropriate correlation of bleeding rate and TTR are calculated.

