all-cause death, ischemic stroke, systemic embolism, or device- or procedure- related events requiring open cardiac surgery or major endovascular intervention such as pseudoaneurysm repair, AV fistula repair, or other major endovascular repair.

Percutaneous catheter drainage of pericardial effusions, snaring of an embolized device, thrombin injection to treat femoral pseudoaneurysm and nonsurgical treatments of access site complications are excluded from this endpoint.

2. The occurrence of composite events* including stroke (all/ ischemic/ hemorrhagic), systemic embolism and CV death (including unexplained cause) .

*All data collected up to the last patient's 6 months follow-up visit to be completed.

3. The rate of effective LAA closure* at 45 days and 6 months. Change in the rate between the two time points will also be analyzed.

*The effective LAA closure is defined as peri-device flow \leq 5mm demonstrated by TEE. TEE measurements will be assessed by independent Core Lab.

A study to confirm the safety and effectiveness of the BSJ003W in Japanese patients with non-valvular atrial fibrillation at increased risk of thromboembolism in Japanese clinical environment	
Secondary endpoints	
Safety endpoints:
 
 • The occurrence of major bleeding* at 0 – 45 days, 45 days – 6 months, 6 months – 24 months 
*Major bleeding is defined as per BARC bleeding definition type 3 or 5
 
 • Frequency of the following bleeding events at 0 – 45 days, 45 days – 6 months and 6 months – 24 months: • Clinically overt non-fatal bleeding* • All bleeding events 
*Clinically overt non-fatal bleeding is defined as per BARC bleeding definition type 2.
 
Effectiveness endpoints:
 
 • The occurrence of composite events* for effectiveness; stroke (all/ ischemic/ hemorrhagic), systemic embolism and CV death (including unexplained cause) 
*All data collected up to the last patient's 12 months and 24 months follow-up visits to be completed.
 
 • Effective LAA closure at 12-month and its time course until then. • The occurrence of ischemic stroke or systemic embolism (excluding 7 days after implanting or day after hospital discharge whichever is later) at 6 months, 12 months and 24 months.

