Additional Endpoints	
Device performance:
 
 • Technical Success defined as successful delivery and release of BSJ003W into the LAA including successful recapture and retrieval if necessary. 
Safety endpoints:
 
 • Occurrence of reportable adverse events • Occurrence of all-cause mortality 
Effectiveness endpoints:
 
 • Individual occurrence of all-cause death, ischemic stroke,

A study to confirm the safety and effectiveness of the BSJ003W in Japanese patients with non-valvular atrial fibrillation at increased risk of thromboembolism in Japanese clinical environment									
	
hemorrhagic stroke, systemic embolization, cardiovascular death (including unexplained cause) at 6-month, 12-month and 24-month.
 
 • Warfarin discontinuation rate at 45 days, 6-month and 12-month • Severity of stroke assessed by NIH Stroke Score, Modified Rankin Scale Score, and Barthel Index 
Other endpoint:
 
 • EQ-5D 								
Required Medication Therapy	
  
 Visit	Medication	
   
 Implant through 45-day visit	ASA+ Warfarin	
 
 45-day visit through 6-month visit	ASA+ Thienopyridine	
 
 Following the 6-month visit	ASA	
  
 
Warfarin therapy should be appropriately monitored and adjusted so as to achieve a therapeutic INR of 2.0- 3.0. For a subject who are 70 years old or older, a therapeutic INR of 2.0 – 2.6 is recommended considering the high risk of major bleeding. Subjects should remain on warfarin until the 45-day TEE evaluation has shown adequate seal of the LAA. If the LAA is not adequately sealed, the subjects should be on warfarin and Aspirin therapy.
	Visit	Medication	Implant through 45-day visit	ASA+ Warfarin	45-day visit through 6-month visit	ASA+ Thienopyridine	Following the 6-month visit	ASA
Visit	Medication								
Implant through 45-day visit	ASA+ Warfarin								
45-day visit through 6-month visit	ASA+ Thienopyridine								

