Following the 6-month visit	ASA								
Follow-up Schedule	
Study procedures and follow-up visits will occur as follows:
 
 • Informed consent • Screening • BSJ003W Implant • 45-day Follow-up (45 ± 15 days) • 6-Month Follow-up (180 ± 15 days) • 12-Month Follow-up (365 ± 30 days) • 18-Month Follow-up (540 ± 60 days) • 24-Month Follow-up (730 ± 60 days) 								
Study Duration	
The duration of the study is expected to last approximately 3 years. The duration of individual subject participation is expected to last approximately 2 years.
								

A study to confirm the safety and effectiveness of the BSJ003W in Japanese patients with non-valvular atrial fibrillation at increased risk of thromboembolism in Japanese clinical environment	
Key Inclusion Criteria	
 1. The subject is Japanese, over 20 years old and provides written informed consent to participate in the trial 2. The subject has documented paroxysmal, persistent or permanent non-valvular atrial fibrillation 3. The subject has a calculated CHA₂DS₂-VASc score of 2 or greater and is recommended for long-term oral anti-coagulation therapy 4. The subject is deemed by their physicians to be suitable for anticoagulant therapy and have an appropriate rationale to seek a non-pharmacologic alternative to warfarin 5. The subject is eligible to come off warfarin therapy if the LAA is sealed (i.e. the subject has no other conditions that would require warfarin therapy).

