3.1 Primary Safety Endpoint (Endpoint 1)

Primary safety endpoint is the occurrence of one of the following events between the time of implant and within 7 days following the procedure or by hospital discharge, whichever is later:

all-cause death, ischemic stroke, systemic embolism, or device- or procedure-related events requiring open cardiac surgery or major endovascular intervention such as pseudoaneurysm repair, AV fistula repair, or other major endovascular repair.

Percutaneous catheter drainage of pericardial effusions, snaring of an embolized device, thrombin injection to treat femoral pseudoaneurysm and nonsurgical treatments of access site complications are excluded from this endpoint.

Similarities of this study results will be evaluated with foreign pivotal study results.

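### Section 5.8 groups outcomes by closure status at the 45-day and 6-month TEE without limiting the count to later events, so the early endpoint windows are sorted by a finding made after them (exploratory table, minor)

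*SAP*

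**What the plan says.** Section 5.8 sets out to explore how LAA closure relates to the other endpoints, and states that "effective LAA closure rate at 45 days and 6 months will be used to classified other endpoints". It adds that "Descriptive analysis will be used for other analysis". It gives no starting point for counting events, no rule for subjects without a TEE reading, and no display of antithrombotic therapy beside closure status.

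The timing comes from Section 1. The readings belong to the visits given as "45-day Follow-up (45 ± 15 days" and "6-Month Follow-up (180 ± 15 days", that is, days 30–60 and 165–195.

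The endpoint windows are:
- Endpoint 1 (Section 3.1): "between the time of implant and within 7 days following the procedure or by hospital discharge, whichever is later".
- Major bleeding (Section 1): "The occurrence of major bleeding* at 0 – 45 days, 45 days – 6 months, 6 months – 24 months". The other bleeding endpoints use the same windows.
- Endpoint 2 (Section 1): "All data collected up to the last patient's 6 months follow-up visit to be completed".

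On therapy, Section 1 keeps subjects on warfarin until the 45-day TEE shows adequate seal, after which the schedule is ASA plus thienopyridine. It also says: "If the LAA is not adequately sealed, the subjects should be on warfarin and Aspirin therapy".

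**The concern.** A grouping variable observed at day 45 or day 180 can describe what follows it. When events from before the reading are tabulated by it, the table looks like a closure–outcome relationship, but for those events the order in time is reversed. The later status may also reflect who remained in follow-up long enough to be imaged.

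A second difficulty affects events after the 45-day TEE. The finding that places a subject in the closed or not-closed column also guides whether warfarin continues. A difference in bleeding or stroke between the columns could therefore come from the regimen, from the seal, or from both.

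What is at stake is how one exploratory table is read. With very few unclosed subjects, a single misplaced event can determine the whole not-closed column.

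**Working it through.** **1. Order of windows and readings**

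| Window | 45-day reading (day 30–60) | 6-month reading (day 165–195) |
|---|---|---|
| Endpoint 1 | before, unless discharge is later than the TEE | before, with the same exception |
| Bleeding 0–45 days | essentially before | before |
| Bleeding 45 days–6 months | after, apart from the visit window | essentially before |
| Endpoint 2, subject's first 6 months | partly before | essentially before |
| Bleeding 6–24 months | after | after, apart from the visit window |

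Endpoint 2 is cut at the last patient's 6-month visit, so subjects enrolled early also contribute events after their own 6-month TEE. Those events are in the right order.

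**2. Share of follow-up before the reading**

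The SAP gives no event counts. If the event rate is assumed constant over time (my assumption), the share of events before the reading equals the share of days before it:
- 45-day reading: 45/180 = 25% at 6 months (30/180 = 17% to 60/180 = 33% across the visit window), 45/365 = 12% at 12 months, 45/730 = 6% at 24 months.
- 6-month reading: 180/180 = 100%, 180/365 = 49%, 180/730 = 25%.

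Conversely, 730 − 45 = 685 days follow the first reading and 730 − 180 = 550 follow the second. Procedure-related events cluster early, so a constant rate probably understates the share before the 45-day reading.

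**3. Size of the not-closed group**

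Inputs from Sections 1 and 3.2.2: 40 subjects, 10% attrition to the 6-month TEE, expected closure 99.3%, lower bound 97.3%, target 94.0%, up to 2 unclosed allowed.

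The plan's own figure reproduces. 40 × 0.90 = 36 subjects with a TEE. With 2 unclosed, 34/36 = 94.4%, which exceeds 94.0%. The exact binomial P(at most 2 unclosed of 36 | 0.7%) = 0.998, which meets the stated 95%.

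The same inputs applied to Section 5.8:

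| Closure rate | Expected unclosed of 36 | P(none unclosed) |
|---|---|---|
| 99.3% | 36 × 0.007 = 0.25 | 0.993^36 = 78% |
| 97.3% | 36 × 0.027 = 0.97 | 0.973^36 = 37% |
| 94.0% | 36 × 0.060 = 2.2 | 0.940^36 = 11% |

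With the two unclosed subjects that the plan allows, the exact 95% interval for an event rate in that group is 0–84% for 0/2 and 1–99% for 1/2.

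**4. Whether another section repairs this**

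- Section 5.3 uses ability to discontinue warfarin as a subgroup factor, but does not cross it with closure.
- Section 5.5 lists warfarin discontinuation as a covariate. Closure is not in that list, so the model does not separate the two.
- Section 5.6 provides worst-case and tipping-point analyses for the binary primary endpoints, if necessary. It is not linked to Section 5.8.
- Section 1 restricts event time for one secondary endpoint (ischemic stroke or systemic embolism, excluding the early period). Section 5.8 has no such restriction.

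**The case against.** The strongest reply is that nothing rests on this table. Section 3 declares success on the 10% safety target and the 94% closure target alone, Sections 3.1.1 and 3.2.1 state no hypotheses, and Section 5.8 speaks of exploring a relationship, not of an effect. That stands, and it is why the point is minor.

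It can also be said that Section 5.8 does not name the other endpoints, and that Section 1 labels only EQ-5D as such. The natural reading is endpoints other than closure, and Section 5.1, under a similar title, includes primary and secondary endpoints. Still, tabulating Endpoint 1 by closure is an inference from open wording.

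Bleeding is already split by period, so much of it can be read in the right order without any change. That also stands, apart from the ±15-day visit windows.

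Finally, sparsity limits the comparison more than time order does. At 99.3% closure there is a 78% chance that no subject is unclosed at 6 months, and no counting rule cures that. This is right. It argues against splitting further by warfarin status, which would give near-empty cells, and in favour of a listing.

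**Conclusion.** The concern holds in a limited form. As written, Section 5.8 lets Endpoint 1, 0–45-day bleeding and, for the 6-month reading, nearly all events of the first 180 days be grouped by a status observed afterwards. Restricting the count to later events is a better method than the one stated. The size is minor, because the analysis is exploratory and descriptive and the primary conclusion is unaffected.

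Three stronger readings are tempting, and the SAP does not support them:
- A reader might infer that the closure–outcome relationship cannot be read at all. Most of the 24 months follows each reading, and events in that time are not affected by the time-order problem.
- A reader might equate closed versus not closed with off versus on warfarin. The SAP does not say that adequate seal means Core Lab flow of 5 mm or less, and it ties the warfarin decision to the 45-day TEE, not explicitly to the 6-month one. The overlap is large but not shown to be complete.
- A reader might infer that subjects who die or leave before the TEE vanish from the table. Section 7.3.4 ties closure status to imaging at the visit, but Section 5.8 does not say whether such subjects are excluded or shown as missing.

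The conclusion assumes that the other endpoints include the primary and secondary ones. The group sizes rest on the SAP's closure rates and 10% attrition.

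**What to change.** Reword Section 5.8 as follows:
1. For each TEE, count only events and follow-up after the TEE date, in subjects with a Core Lab reading who are still in follow-up.
2. Do not classify Endpoint 1 or 0–45-day bleeding by closure.
3. Report separately the number of subjects without a reading, and their events.
4. Do not stratify further by warfarin. List each not-closed subject with TEE date, antithrombotic regimen and event dates.
5. Flag events whose onset date was imputed under Section 5.7. Those rules move a date to the procedure date or to the start of the month or year, and so can place an event on the wrong side of a TEE.

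The cost is SAP wording and table programming; TEE, event and medication dates are already needed for other planned analyses. The downside is fewer events in an exploratory table.

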7.3.5 Time in Therapeutic range (TTR)

To explore appropriateness of Warfarin control and/or explore the relationship between bleedings, TTR is calculated by Rosendaal Method. (under linear assumption of INR change, then percentage of total of “within therapeutic range time “out of “Time between visits” is calculated.)

The normal ranges of INR are refer to 2.0-3.0 for age less than 70 years, and to 1.6-2.6 for age 70 years old or older in accordance with JCS guideline, and also for a subject 70 years old or older, a recommended range is to 2.0-2.6 in SALUTE protocol consideration.

End of file

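### Bleeding is related only to percentage time in range, which counts low and high INR alike, and the INR window is not fixed relative to the bleed

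*SAP*

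**What the plan says.** SAP section 5.8 lists, among exploratory analyses, a description of TTR and a correlation with bleeding: "an appropriate correlation of bleeding rate and TTR are calculated". The coefficient is not named, and neither is the bleeding window to be paired with TTR. The rest of that section is covered by "Descriptive analysis will be used for other analysis".

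Section 7.3.5 gives the purpose and method: "To explore appropriateness of Warfarin control and/or explore the relationship between bleedings, TTR is calculated by Rosendaal Method". The quantity derived is one percentage: "percentage of total of “within therapeutic range time “out of “Time between visits” is calculated". The SAP nowhere derives time below or time above range. It gives no start or end date for the INR series and no rule for INR values after a bleed.

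The relevant exposure is short for most subjects. Section 1 (Required Medication Therapy) states: "Subjects should remain on warfarin until the 45-day TEE evaluation has shown adequate seal of the LAA". Warfarin continues only where the seal is inadequate. Bleeding, by contrast, is reported for 0-45 days, 45 days to 6 months and 6 to 24 months.

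**The concern.** Two features make the planned correlation hard to interpret.

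**Direction is lost.** Time below the lower limit and time above the upper limit reduce TTR by the same amount, although one would expect them to act on bleeding in opposite ways. Section 1 itself treats the upper limit as relevant to bleeding: it cites bleeding risk when it gives subjects aged 70 or older a recommended range of 2.0-2.6 instead of 2.0-3.0, and the two differ only at the top. Subjects whose TTR is low because of low INR weaken any link that runs through high INR.

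**Order in time is open.** If warfarin is held or reversed after a bleed, later INR values fall below range and TTR falls with them. A link between low TTR and bleeding could then appear even where control before the bleed was good.

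Section 2 allows the planned analyses to be used in presentations and manuscripts, so a TTR-bleeding correlation could be quoted without these limits.

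**Working it through.** The SAP gives no figure for this correlation, so there is none to reproduce. The direction point follows from the definition in 7.3.5. The INR values and distributions below are assumptions chosen to show the mechanism. The range is 2.0-3.0 unless stated.

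**1. Same TTR, opposite direction (linear path over 45 days)**
- INR 1.4 to 2.6: in range (2.6 − 2.0)/1.2 = 50%; above range 0%.
- INR 2.4 to 3.6: in range (3.0 − 2.4)/1.2 = 50%; above range (3.6 − 3.0)/1.2 = 50%.

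With INR at days 0, 7, 14, 21, 28 and 45, two mirror-image series behave the same way. The series 2.5, 2.5, 3.5, 3.5, 2.5, 2.5 is above range for 3.5 + 7 + 3.5 = 14 days, and 14/45 = 31.1%. The series 2.5, 2.5, 1.5, 1.5, 2.5, 2.5 is below range for the same 31.1%. TTR is 68.9% for both.

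**2. Dilution (simulation, 200,000 subjects)**

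Out-of-range fraction is Beta(2,3). A varying share of it is high, and the log-odds of bleeding is −3 + 5 × the fraction of time above range, so bleeding depends on high INR only. Correlations with bleeding:
- 20% of out-of-range time high: TTR −0.07, time above range 0.16.
- 50% high: TTR −0.19, time above range 0.28.
- 80% high: TTR −0.32, time above range 0.37.

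TTR is weaker each time. The gap narrows as more of the out-of-range time is high.

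**3. INR values after a bleed**
- Simple case: 80% in range, bleed on day 15, 15 days below range, then 80% again. TTR = (0.8 × 15 + 0 × 15 + 0.8 × 15)/45 = 24/45 = 53%, against 80% before the bleed.
- Interpolated case: INR 2.5, 2.6, 2.7, 1.2, 1.3, 2.2 on the same visit days, with a bleed on day 14. TTR to day 14 is 100%. Over 45 days it is 46.8%, with 53.2% below range and 0% above. The split shows what TTR hides: the lost time is all on the low side.
- Simulation: bleeding in 15%, independent of earlier INR, at a uniform time over 45 days; fraction in range Beta(6,3) before the bleed and Beta(2,6) after it. The correlation with full-period TTR is −0.44; with pre-bleed TTR it is 0.00.

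**4. Precision with 40 subjects**

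The approximate 95% half-width of a correlation near zero, on the Fisher z scale, is 1.96/√(40 − 3) = 0.32. Most of the differences in step 2 are smaller than this, so the gain is in interpretability more than in detection.

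**5. The two ranges for age 70 or older**

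Section 7.3.5 names 1.6-2.6 and also says that "a recommended range is to 2.0-2.6 in SALUTE protocol consideration", without saying which one defines TTR. For INR 1.8, 1.7, 1.8, 2.1, 2.3, 2.4 on the same visit days, TTR is 100% under the first and 58.5% under the second. Both ranges end at 2.6, so time above range is the same under either.

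**The case against.** The strongest reply is that TTR does what 7.3.5 asks of it. The stated purpose is appropriateness of warfarin control and/or its relation to bleeding, and percentage time in range summarises quality of control. Over-anticoagulation is not a named aim, so leaving out time above range contradicts nothing in the SAP. That stands: this is a better choice of exploratory variable, not an error.

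Two stronger readings are tempting, and the SAP supports neither.
- A reader might infer that TTR includes INR values after a bleed. The SAP does not say so. Dividing by the time between visits, with no cut at a bleed, permits inclusion and makes it a likely programming default, but the text is silent. The supportable point is that the window is not fixed.
- A reader might infer that the correlation can show nothing about high INR and bleeding. Step 2 of the working shows a diluted link, not an absent one.

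The reverse-direction concern is also limited to bleeds during warfarin treatment. For a bleed after warfarin has stopped, the INR time comes first, and the open question is which bleeding window is paired with TTR.

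Finally, cutting the INR series only in subjects who bleed has its own bias. It compares short early windows with full-period windows, so drift in INR control over time could look like a link with bleeding, and a subject who bleeds before a second INR has no interval to interpolate. This is a good reason to keep the cut as a sensitivity analysis.

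**Conclusion.** The point holds as a minor improvement to an exploratory analysis. That TTR merges low and high INR time follows from 7.3.5 and needs no assumption. How far this weakens the correlation depends on the mix of low and high INR, which the SAP does not give; in the assumed scenarios it ranges from slight (−0.32 against 0.37) to marked (−0.07 against 0.16).

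The possibility that the bleed lowers TTR is not excluded, because the window is not fixed. It matters only for bleeds on warfarin and only if warfarin is held or reversed; the −0.44 is a product of its assumptions. No primary or secondary endpoint and no performance target depends on this analysis.

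**What to change.** - **Section 7.3.5:** derive percentage of time below, within and above range from the same Rosendaal interpolation. State the start and end of the INR window. Reconcile the two ranges for subjects aged 70 or older, so that one is named as defining TTR.
- **Section 5.8:** relate bleeding during warfarin treatment to percentage of time above range, with TTR and time below range alongside. Name the correlation measure and the bleeding window.
- **Sensitivity analysis:** repeat with INR values up to first bleed onset. Report the shorter windows in subjects who bleed, and the number left without an INR interval. This includes any subject whose wholly missing onset date is set to the procedure date under section 5.7.

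The cost is SAP wording, two more derived variables and one more exploratory table. No additional samples or visits are needed. With about 40 subjects the results remain descriptive.
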